5.3.1 Adverse Event Reporting Period

Investigators will seek information on AEs at each patient contact. All AEs, whether reported by the patient or noted by study personnel, will be recorded in the patient's medical record and on the Adverse Event eCRF.

After informed consent has been obtained but prior to initiation of study drug, only SAEs caused by a protocol-mandated intervention should be reported (e.g., SAEs related to invasive procedures, such as biopsies).

After initiation of study drug, all AEs, regardless of relationship to study drug, will be reported until the common closeout date and during extended follow-up (if applicable). After this time, investigators should report any deaths, SAEs, or other AEs of concern that are believed to be related to prior treatment with study drug (see Section 5.6).

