5.3.6.2 Deaths

All deaths that occur during the protocol-specified AE reporting period (see Section 5.3.1), regardless of relationship to study drug, must be recorded on the Adverse Event eCRF and immediately reported to the Sponsor (see Section 5.4.2). This includes death attributed to progression of GPA or MPA.

Death should be considered an outcome and not a distinct event. The event or condition that caused or contributed to the fatal outcome should be recorded as the single medical concept on the Adverse Event eCRF. Generally, only one such event should be reported. The term “**sudden death**” should only be used for the occurrence of an abrupt and unexpected death due to presumed cardiac causes in a patient with or without preexisting heart disease, within 1 hour of the onset of acute symptoms or, in the case of an unwitnessed death, within 24 hours after the patient was last seen alive and was stable. If the cause of death is unknown and cannot be ascertained at the time of reporting, “**unexplained death**” should be recorded on the Adverse Event eCRF. If the

cause of death later becomes available (e.g., after autopsy), “unexplained death” should be replaced by the established cause of death.

If the death is attributed to progression of MPA/GPA, MPA/GPA “progression” should be recorded on the Adverse Event eCRF.

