1. BACKGROUND

This document provides specifications for the primary analysis including, remission induction phase, follow-up phase and extended follow-up phase, of the study WA25615.

- **Remission Induction Phase:** Day 1 until end of month 6.
- **Follow-Up Phase:** Post month 6 until common closeout date, where common closeout date is 18 months after the enrolment of the last patient.
- **Extended Follow-Up Phase:** Post common closeout date until CD19 B-cell counts have returned to baseline level or within normal range, whichever is lower.

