2.3.1 Data Included in the Remission Induction Phase

The following data will be included in the analysis of the 6-month time-point:

- **Patients entering the follow-up phase:**
 - All screening and post-baseline data with a clinical date (i.e., administration/assessment/onset/start date) on or before the date of entry into the follow-up phase at Month 6 will be included.

The only exceptions to this is:

- Concomitant medications that begin on the date of entry to the follow-up phase will not be included.
- **Patients not entering the follow-up phase:**

All screening and post-baseline data with a clinical date on or before the date of the patient's last study visit within Study Day 210 will be included; (Day 210 equals 180 days plus a 30-day window).

The data cut will include all data regardless of the type of study visit at which it was collected. This may include data collected at unscheduled visits, dosing termination visits, early termination visits, or safety follow-up visits, if the visit date was on or before the data cutoff date.

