2.3.2 Data Included in the Follow-up Phase

For patients who enter the Follow-up phase all of their screening data plus post Month-6 data with a clinical date on or before the date of entry into the Extended Follow-up Phase will be included in this analysis of the Follow-up phase.

- **Patients entering the extended follow-up phase:**
All screening and post-Month-6 data with a clinical date on or before the date of entry into the extended follow-up phase will be included.
- **Patients not entering the extended follow-up phase:**
All screening and post-Month-6 data with a clinical date on or before the date of the patient's last study visit within common closeout date will be included.

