3.4 Analysis Overview

Safety Analyses

All safety analyses will be done on safety population and by study phase.

Abnormal electrocardiogram (ECG), chest X-ray and chest CT scan findings are to be reported.

Details of the analyses and outputs are given in Section [5](#) to [9](#).

Efficacy Analysis

[REDACTED]

[REDACTED]

Pharmacodynamic Analyses

[REDACTED]

Subgroup Analyses

The sample size for this study is too small to permit subgroup analyses.

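### For a patient who does not enter the next phase, the SAP cuts AEs at the last study visit, so a later AE is in no by-phase data set; the visit list of AE002.2SP also contradicts its own stated period

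*SAP*

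**What the plan says.** SAP 1 defines the phases by calendar: induction is "Day 1 until end of month 6" and follow-up is "Post month 6 until common closeout date". SAP 3.4 adds: "All safety analyses will be done on safety population and by study phase".

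SAP 2.3 then sets which data enter each phase. A patient who goes on to the next phase is cut at the date of entry. For a patient who does not enter follow-up, SAP 2.3.1 takes data up to the patient's "last study visit within Study Day 210 will be included". For a patient who does not enter extended follow-up, SAP 2.3.2 takes data up to the "last study visit within common closeout date will be included". The dating rule is "clinical date (i.e., administration/assessment/onset/start date", so an AE is dated by its onset. Unscheduled and early termination visits count as visits. The follow-up and extended follow-up data sets (SAP 2.3.2 and 2.3.3) hold only patients who enter those phases.

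The protocol's reporting period is longer. Under 5.3.1, after the first dose, "all AEs, regardless of relationship to study drug, will be reported until the common closeout date", and also during any extended follow-up. Protocol 5.3.6.2 begins "All deaths that occur during the protocol-specified AE reporting period" and requires each to be recorded and reported at once; it treats death as the outcome of an AE.

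On infusion-related reactions (IRRs), AE002.2SP has one table for induction and one for an overall period from Day 1 to common closeout, with infusion numbers as columns. It then restricts the visits to Baseline, Weeks 1 to 3 and Months 6, 12 and 18. Retreatment after Month 6 has no fixed schedule (protocol 4.3.4, SAP 2).

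**The concern.** The frequency, nature and severity of AEs is a primary outcome, and safety is to be reported by phase. A cut at the last visit works for values measured at visits. It does not suit AEs, which start between visits. The patient whose record is cut short is the one who has no further visit, and a death between visits is the clearest case. The 6-month interim analysis and the induction tables could then omit a fatal event that began in the induction phase.

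The IRR point is of the same kind. EX001.1SP counts infusions from Day 1 to common closeout. If AE002.2SP keeps only infusions at the listed visits, two tables with the same stated period can rest on different numbers of infusions.

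**Working it through.** **The plan's own figure.** SAP 2.3.1 derives its cap as 180 + 30 = Day 210. This reproduces, and it matches the upper end of the Month 6 window in SAP 3.3 (Days 165–210).

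**Applying the phase rules to two test cases.**
- Last visit Day 60, fatal AE with onset Day 90, patient never enters follow-up. Induction: 90 > 60, excluded. Follow-up and extended follow-up: not entered, excluded. By SAP 1 the event lies inside induction.
- Patient enters follow-up, last visit Day 270, fatal AE with onset Day 330, before closeout. Induction: after Month 6, excluded. Follow-up: 330 > 270, excluded. Extended follow-up: not entered, excluded. By SAP 1 the event lies inside follow-up.

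**How long the exposed interval can be.** From the visit days and windows in protocol Appendix 2, the longest gap is (next day + its window) − (previous day − its window):
- Month 2 to 4: (120 + 5) − (60 − 3) = 68 days
- Month 4 to 6: (180 + 5) − (120 − 5) = 70 days
- Month 6 to 9: (270 + 10) − (180 − 5) = 105 days
- Month 9 to 12: (365 + 10) − (270 − 10) = 115 days
- Months 12 to 15 and 15 to 18: 90 + 10 + 10 = 110 days each

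**What one patient does to an induction incidence, N = 25** (exact Clopper–Pearson 95% limits):
- 0/25: upper limit 1 − 0.025^(1/25) = 13.7%
- 1/25 = 4.0%: limits are the 2.5% point of Beta(1, 25) and the 97.5% point of Beta(2, 24), 0.1% to 20.4%

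**Where the event still appears.** AE021SP takes every AE with onset from first dose to common closeout and has no last-visit cut, so both test events are in it. It has no phase split, so it does not put the first one back into induction.

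**AE002.2SP.** This step assumes that the SAP 3.3 windows, which are written for assessments, are what assigns infusions to the listed visits. The windows are Month 6 = 165–210, Month 12 = 335–395 and Month 18 = 500–590. Not covered after Month 6:
- Days 211–334: 334 − 211 + 1 = 124 days
- Days 396–499: 499 − 396 + 1 = 104 days
- every day after 590

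Over Days 181–545 the listed visits cover 365 − 124 − 104 = 137 of 365 days (37.5%). This is a share of days, not of infusions. For illustration only, assume four weekly infusions in a repeat course. Started on Day 270 (270, 277, 284, 291), none falls in a listed window; started on Day 365 (365, 372, 379, 386), all four do.

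**The case against.** The best reply on the phase cut is that the case is rare and may be rarer than it looks. Patients who stop rituximab stay in the study (protocol 3.1.8). Those who leave for non-compliance or withdrawn consent are asked to a withdrawal visit (4.5.7). Protocol 4.6.1 lists death among the reasons for withdrawal and asks for a complete final evaluation. All of this narrows the gap. It does not close it: the SAP does not say that an evaluation after a death counts as a visit, and a patient lost to follow-up may have none.

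It is also fair that the named AE tables are headed for induction and overall, with no follow-up-only AE table, so the cut in SAP 2.3.2 touches no named AE output. SAP 6 does promise AE summaries by phase, so the rule still needs correcting, but the practical weight lies on induction.

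A reader might infer that such deaths vanish from the report. The documents do not support that: AE021SP keeps them, and AE023.2SE tabulates fatal SAEs with no phase or last-visit cut stated. Nor would AE021SP and the induction table contradict each other over one period, because AE021SP covers a longer one.

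A reader might also want deaths assigned to a phase by date of death, since that date is not among the named clinical dates. That would split one event. With onset on Day 175, entry to follow-up on Day 180 and death on Day 200, AE005SP would place the fatal AE in induction while the death count in AE001SP for induction would be zero. Protocol 5.3.6.2 and the onset rule in SAP 2.3.1 already point to one phase.

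On AE002.2SP, the infusion-number columns, and a mock-up that runs to later infusions, allow the reading that every infusion is meant. On that reading the visit list has no function in the overall table, so the specification still contradicts itself.

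**Conclusion.** The point holds in a limited form and should be fixed. An AE that starts after the last visit of a patient who does not enter the next phase is omitted from the by-phase data sets, against the phase definitions in SAP 1 and the reporting period in protocol 5.3.1. The visible effect is on the 6-month interim analysis and the induction-phase AE tables; one patient moves an incidence from 0/25 to 1/25, or 4 percentage points. It is an omission from the phase tables and not a total loss. That the case is mainly fatal AEs, or patients lost to follow-up, is an inference from the visit rules. The documents do not give the number of such events.

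AE002.2SP is inconsistent as written. A reader might infer from the 37.5% day coverage that most retreatment IRRs would be dropped. That does not follow: retreatment timing is left to the investigator, the day ranges hold only if the SAP 3.3 windows are applied to infusions, and the number omitted cannot be derived.

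The lack of a stated window for the other AE tables labelled Overall (AE001SP, AE002SP and the subset tables) is a missing detail only. No competing window is given.

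**What to change.** 1. In SAP 2.3.1 and 2.3.2, for AEs of patients who do not enter the next phase, replace the last-visit cut with onset on or before the phase end: Day 210 for induction, common closeout for follow-up. The cut at entry for patients who do go on stays as it is.
2. State that a fatal AE and its death both belong to the phase of the AE's onset, so that AE001SP and AE005SP agree.
3. Leave the last-contact definition in EX001.1SP unchanged. Its date of last contact may be a recorded date, and dropping it could lose the latest information on a patient lost to follow-up.
4. In the overall table of AE002.2SP, replace the visit list with every rituximab infusion from Day 1 through common closeout, so that it rests on the same infusions as EX001.1SP.
5. As a minor clarification, state the same Day 1 to closeout window for the other AE tables labelled Overall.

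The cost is SAP wording and a little reprogramming. No new data are collected and patient management does not change. AE counts in the phase tables may rise slightly.

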2.3.2 Data Included in the Follow-up Phase

For patients who enter the Follow-up phase all of their screening data plus post Month-6 data with a clinical date on or before the date of entry into the Extended Follow-up Phase will be included in this analysis of the Follow-up phase.

- **Patients entering the extended follow-up phase:**
All screening and post-Month-6 data with a clinical date on or before the date of entry into the extended follow-up phase will be included.
- **Patients not entering the extended follow-up phase:**
All screening and post-Month-6 data with a clinical date on or before the date of the patient's last study visit within common closeout date will be included.

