4.3.2.3 Prednisolone or Prednisone (Non-Investigational Medicinal Product)

4.3.2.3.1 Dosage, Administration, and Compliance

On Day 1 and following completion of IV glucocorticoids, all patients will receive concomitant oral prednisolone or prednisone (1 mg/kg/day or up to 60 mg/day or equivalent, whichever is lower), the dose of which will be tapered to a minimum of 0.2 mg/kg/day (or 10 mg/day, whichever is the lowest) no later than Month 6.

The general guidance on the suggested oral steroid dose-tapering schedule is to taper from 1 mg/kg/day (60 mg/day, maximum) at the start of treatment, to 0.8 mg/kg/day by Month 1, and then by 0.1–0.2 mg/kg/day each month to 0.2 mg/kg/day (or 10 mg/day, whichever is the lowest), which should be reached no later than Month 6.

Oral prednisone (used in some non-UK sites) may be substituted for prednisolone at the same dose as long as there is no hepatic impairment.

The steroid-tapering practice is specific to a particular patient and as such should be tailored individually for each patient at the time of study entry, at the discretion of the investigator.

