4.1 Analysis of Study Conduct

The following data will be summarized for the safety population, giving the number and percentage of patients who:

- Had major protocol deviations occurring during the remission induction phase
- Were withdrawn prematurely from the study
- Entered extended follow-up (To be added later as CSR addendum)
- Entered extended follow-up
- Switched to local standard care during the study by study phase

In addition, summaries will be provided of:

- Non-study treatments given for GPA and MPA by study phase
- Concomitant medications received by study phase

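### The by-phase medication summaries place drugs by start date, so non-steroid drugs begun between Day 1 and Month 6 and still running drop out of the follow-up phase

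*SAP*

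**What the plan says.** Three parts of the SAP have to be read together.

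- **Section 2.3.1** (remission induction phase) gives the date by which a record is cut: "clinical date (i.e., administration/assessment/onset/start date". Its one exception shows how medications are handled at the boundary: "Concomitant medications that begin on the date of entry to the follow-up phase will not be included".
- **Section 2.3.2** (follow-up phase) uses the same term. For children who go on to extended follow-up: "All screening and post-Month-6 data with a clinical date on or before the date of entry into the extended follow-up phase will be included". For the others the lower limit is the same, and the upper limit is their last visit up to common closeout. Section 2.3.3 admits screening data plus data from after the follow-up phase.
- **Section 4.1** plans two medication summaries that depend on these rules: "Non-study treatments given for GPA and MPA by study phase" and "Concomitant medications received by study phase". It also plans a patient count, "Switched to local standard care during the study by study phase". That count concerns an event, so dating it by when it happens is reasonable, and it is not part of this point.

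None of these sections uses a stop date or says what to do with a treatment that spans a phase boundary. No other visible text gives the Section 4.1 summaries a different rule.

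**The concern.** An adverse event or an infusion happens on a date, and assigning it to a phase by that date is sound. A medication runs over an interval. If it is assigned by its first day alone, a drug begun in induction and continued for the whole of follow-up is counted only in induction.

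The protocol provides for this situation. Before or by Month 6, Protocol 3.1.2 and 4.5.9 allow treatment under local standard of care for children who do not complete the four infusions, who flare beyond what glucocorticoids can control, or who have progressive disease. These children stay in the study. Protocol 4.4.2.1 then allows maintenance after Month 6 with several immunosuppressants, so a drug already begun may well be continued.

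At stake is the description of background treatment. SAP Section 3.4 says safety analyses are done by study phase, and infections or low counts in follow-up are read against the immunosuppression given at that time. A follow-up summary that omits current drugs, and may include stopped ones, gives the wrong background.

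**Working it through.** The documents state no figure on this point, so there is none to reproduce. The check applies the written rules to hypothetical medication records and compares the result with an overlap rule.

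**Inputs**

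- Date attached to a record: administration, assessment, onset or start date (SAP 2.3.1).
- Medications beginning on the date of entry to follow-up are excluded from induction (SAP 2.3.1).
- Follow-up data set: screening data plus post-Month-6 data (SAP 2.3.2).
- Entry to follow-up at Day 180, the planned Month 6 day in SAP Table 1.
- Phase end at Day 545, the planned Month 18 day. Taking Days 180 and 545 as the phase limits is an assumption for illustration; actual dates differ by child.

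**Rules**

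- Literal, induction: recorded at screening, or start < 180.
- Literal, follow-up: recorded at screening, or 180 < start ≤ 545.
- Overlap, follow-up: start ≤ 545, and stop missing or after Day 180. No test record stops on Day 180, so counting a stop on that day would change nothing here.

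**Results**

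| Hypothetical record | Literal: induction | Literal: follow-up | Overlap: follow-up |
|---|---|---|---|
| Immunosuppressant begun Day 120, ongoing | in | **out** | in |
| Recorded at screening (begun Day −60), ongoing | in | in | in |
| Recorded at screening (begun Day −60), stopped Day 30 | in | **in** | out |
| Begun Day 180 (entry date), ongoing | out | **out** | in |
| Begun Day 200, ongoing | out | in | in |

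The literal and overlap rules disagree in three of the five cases, and in both directions.

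1. A drug begun after Day 1 and before Month 6 and still running (120 < 180) is left out of follow-up.
2. A drug recorded at screening and stopped on Day 30 is kept in follow-up, because all screening data are kept.
3. A drug begun on the entry date is removed from induction by the exception in 2.3.1. It is also outside follow-up if post-Month-6 means strictly after that date.

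Section 2.3.3 has the same structure, so a drug begun in follow-up and still running would be left out of extended follow-up. The effect there is narrower: Protocol 3.1.4 ends follow-up for a child who receives an agent affecting B-cell return on or after the common closeout date. It therefore concerns mainly other drugs.

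**The case against.** **The rule may be looser than this reading.** In Section 2.3.2 the clinical date formally sets only the upper limit. The lower limit, post-Month-6 data, is undefined. The definition in 2.3.1 also includes an administration date, and a continuing drug is administered after Month 6. This stands in part: exclusion is the natural reading but not the only one. Against it, the exception in 2.3.1 places concomitant medications by the day they begin. The CM003SP mockup also shows a medication record with a start and a stop date and no date for each dose. If the text were merely ambiguous, two programmers could produce different tables, and the same correction would be needed.

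**The information is elsewhere.** Listings CM003SP and CM003.2SP (SAP 4.3) include drugs whatever their start date if they run on during the study, and the mockup they share shows start and stop dates. With 25 children a reader can find concurrent treatment there. This stands, and it is the main reason the point is minor. The listings are not split by phase, though, and they do not correct a wrong summary.

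**Steroids.** A reader might infer that every child is affected, since "On Day 1 and following completion of IV glucocorticoids, all patients will receive concomitant oral prednisolone or prednisone", and a record starting on Day 1 fails the follow-up rule. The documents do not support this. Oral prednisolone or prednisone is protocol background therapy (Protocol 4.3), so it is not obviously a non-study treatment. It also has its own outputs beyond Month 6: follow-up duration categories in SAP 5.1, EX003SP for induction and overall, listing EX004SP with start and end days, the EX007SP profiles, and EX007.1SP to EX007.3SP up to Month 18.

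**Events on rituximab alone.** A reader might infer that later infections would appear to have occurred on rituximab alone. That would require a child with no other qualifying record and a reader who looks only at the summary. No shell for the by-phase medication summaries is visible. Most visible adverse-event shells are titled for induction and overall, and none is for follow-up alone, although SAP Sections 3.4 and 6 do say by study phase.

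**Conclusion.** Wrong as written, on the natural reading of SAP 2.3.1 and 2.3.2 together; minor in severity. The defect is confined to the two by-phase medication summaries in SAP 4.1 and to non-steroid drugs. No data are lost from the report. Adverse-event and laboratory frequencies and the PK parameters do not depend on the rule, and no hypothesis is tested.

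The broader statement that every drug begun before Month 6 disappears would be too strong, because records made at screening are kept. The gap concerns starts from Day 1 to Month 6, with the entry date itself unresolved.

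The number of children affected cannot be derived. The documents do not say how many will begin a non-steroid drug in that interval and continue it, and any count out of 25 would rest on an assumed rate. The conclusion assumes that a medication record is placed by its start date, as the exception in 2.3.1 indicates, and that no unseen specification overrides this for the Section 4.1 summaries.

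**What to change.** For the two medication summaries in SAP 4.1, add a rule for interval data:

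- Count a medication in every phase that its start-to-stop interval overlaps: start on or before the phase end, and stop missing or on or after the phase start.
- Apply the same test to records made at screening, so that a drug stopped in induction does not appear in follow-up, and to extended follow-up in Section 2.3.3.
- State which phase holds a medication begun on the Month 6 entry date, so that it falls in one phase and not in neither.
- Keep the present onset or administration-date rule for adverse events and infusions.

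The cost is a few lines of SAP text and one condition in the program. Data collection and patient care do not change.
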